### 1. Research questions

RQ1.1: Did the multistep CQI process support changes in primary workshop dosage, program attrition rates, or survey response rates at the program level?

RQ2: Did meaningful improvements in primary workshop dosage, survey response rates, or program attrition rates vary by service site *for sites that focused on improving the same metrics?*

RQ3 [secondary]: Do participants report healthier partner relationship attitude outcomes after program participation, as compared to baseline?

RQ4 [secondary]: Was level of dosage associated with reporting healthier partner relationship attitude outcomes after program participation, as compared to baseline?

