### 2. Outcomes evaluation enrollment

This study was initially approved by Solutions IRB on 03/29/2021 and has been annually reviewed and approved on 03/15/2022, 03/07/2023, and 3/11/2024. Additionally, revisions to the study were submitted as amendments and were approved on 05/17/2022, 02/15/2023, and 08/29/2023.

Participants for the program, and thus the study, are recruited primarily from community partnerships, walk-ins to Anthem Strong Families, radio and social media advertising, and word of mouth referrals.

Program service locations have varied throughout the implementation of the program but have included:

---

- Schools
  - Stephen C. Foster Elementary School
  - Herbert Marcus Elementary School
  - Burnet Elementary School
- Treatment Centers / Transitional Facilities
  - Soul's Harbor Treatment Center
  - Free Man House Transitional Living Facility
  - Shurrun's House Sober Living Facility
  - Gateway Foundation Treatment Center
- Vickery Meadow Youth Development Foundation
- Buckner Children and Family Services, Family Hope Center at Bachman Lake
- Virtual services provided via Zoom

The projected enrollment and desired sample size for the study is 800 participants. The final report will include a breakdown of the number of sites, number of staff at each site, and number of participants at each site.

To be eligible for the program, and thus the study, participants must be 1) low-income individuals, 2) at least 18 years of age, 3) with no open criminal cases (can be deferred), and 4) able to speak and understand English or Spanish.

Consent for enrollment into the evaluation happens during program orientation, prior to the start of the first primary workshop. A consent form is provided to participants, and a script is read by either the facilitator or the data manager, explaining the study activities and the potential risks and benefits. Participants sign and date the consent form and return it to the data manager, who logs the record in a consent spreadsheet on MER's secure Dropbox.

Enrollment into the study began April 22, 2021 and is estimated to conclude February 15, 2025.

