#### 4. Outcome measures

The main outcomes of interest addressed by the multistep CQI process are primary workshop dosage, participant attrition rates, and nFORM survey response rates, as these are key program performance metrics with targets set by the federal funders. The first research question looks at changes in each of these metrics over time overall across all service sites (program level), and the second research question looks at changes in each of these metrics over time broken down by service site for sites that focused on the same metrics. This will involve an assessment of any changes in metrics after intervention strategies were implemented, including whether performance targets were reached and whether improvements were meaningfully large. Potential ceiling and floor effects are mitigated during the process of selecting which metrics to attempt to improve via intervention strategies (i.e., metrics that are already at or close to targets are not selected for intervention); however, potential ceiling and floor effects will also be addressed by providing baseline data for metrics targeted for interventions at each service site.

The secondary research questions about participant-level attitude changes after program participation are assessed by constructing a composite measure calculated as the average of five nFORM survey items related to partner trust and intimacy. If more than one survey item within the composite is missing for a respondent, the value of the outcome measure will be set to missing.

**Table 4.** Outcomes used to answer the research questions

Research question	Outcome name	Description of the outcome measure	Source of the measure	Timing of measure
RQ1	Dosage	The outcome measure is the percent of target primary workshop hours received by program participants	nFORM operational report: Primary Workshop Participation Detail	Attendance is recorded after each workshop session
RQ1	Attrition	The outcome measure is the percent of program participants who leave the program without completing at least 90% of primary workshop hours	nFORM operational report: Client Status Summary	Ongoing

Research question	Outcome name	Description of the outcome measure	Source of the measure	Timing of measure

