**Family Champions Project
Statistical Analysis Plan**

Clinicaltrials.gov ID: NCT05298345

September 4, 2024

Analysis approach

To assess the association between the multistep CQI process and the outcome measures, trends in dosage, retention, and survey response rates will be assessed over time since the start of the program. If the CQI process has been effective in identifying and addressing issues that require intervention, we would expect that program implementation would get stronger over time, as measured by progress toward meeting programmatic targets for these measures.

Analytic sample

The analytic sample for RQ1 and RQ2 is made up of the participants who received services at the facilities that received CQI intervention efforts as part of the multistep CQI process. The aggregated dosage, retention, and survey response rate data for these participants will make up the analytic sample.

The analytic sample for the secondary research questions (RQ3 and RQ4) about participant healthy partner relationship attitudes will be defined as participants who have complete baseline and outcome data for the constructed outcome measure (complete case). Because these relationship questions are only shown to participants who report currently being in a romantic relationship, participants can only have complete case survey data if they report being in a relationship at both waves of data collection. As mentioned above, participants will only be included in the analytic sample if they have one or no missing values for the five items used to construct this outcome measure (80% or 100% of non-missing items). Participants who do not meet this threshold will have their outcome value assigned to missing and will not be included in the analytic sample; no imputation is planned for the outcome data.

Data preparation

Program-level and participant-level data will be downloaded as an Excel file using nFORM's data export feature. The data sets will be cleaned and prepared for analysis using the R Studio statistical software package. All files will be exported into R and cleaned separately before data sets are merged into a final, wide format file for analyses using nFORM client ID as the unique identifier for matching programmatic (dosage, client status, survey response rates) and participant survey data.

Analytic approach

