The analysis for this evaluation will be completed using Excel and the R Studio statistical software package. Trends in programmatic outcome measures will be assessed descriptively over time using graphs that show average dosage, attrition, and survey response rates by month since program start among participants who enrolled in that month. Trends in program-level (cross-site) averages will be assessed for improvements over time, and trends in site-level averages will be assessed both for improvements since program start and immediately following the implementation of targeted interventions, which will be noted on the graphs. Site-level averages will be compared across the full study time period. Assuming the continuous, rapid cycle learning and intervention of the multistep CQI process is happening as planned, average metrics are expected to improve over time and immediately following interventions.

For the secondary research question 3 analysis, a change score will be calculated for each complete case respondent using their average at program entry and their average at program exit. We will use paired sample

t-tests to assess the magnitude and significance of mean score changes among program participants in the analytic sample. For the secondary research question 4 analysis, a basic regression model will be used to determine if higher dosage of primary workshop hours is associated with higher average scores on attitudinal items. Findings are considered statistically significant based on a $p < 0.05$, two-tailed test.

Attrition

Sample attrition is not a concern for the programmatic measures assessed for RQ1 and RQ2.

For the secondary research questions, sample attrition is related to program retention, as participants can only have complete case data if they stay in the program to take their nFORM exit survey. Anthem Strong Families staff have implemented numerous strategies to increase participant retention. Retention is tracked on an ongoing basis as part of the bi-weekly CQI team meetings between Anthem and MER staff, so decreases in survey response rates or participant retention can be tracked and addressed in real time as cohorts are enrolled in the program.

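### RQ1 is read from monthly graphs with no estimate of change, no uncertainty limit and no figure for a meaningful improvement, so chance drift can be read as improvement

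*SAP*

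**What the plan says.** Protocol section B.1 poses RQ1.1 as: "Did the multistep CQI process support changes in primary workshop dosage, program attrition rates, or survey response rates at the program level". Section B.4 gives the three metrics equal standing: "The main outcomes of interest addressed by the multistep CQI process are primary workshop dosage, participant attrition rates, and nFORM survey response rates". None is named primary, and Table 4 lists each as its own RQ1 outcome.

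The SAP (Analytic approach) sets the method: "Trends in programmatic outcome measures will be assessed descriptively over time using graphs". At program level the criterion is: "Trends in program-level (cross-site) averages will be assessed for improvements over time". The SAP's Analysis approach ties this to the CQI process. If the process has worked, "we would expect that program implementation would get stronger over time, as measured by progress toward meeting programmatic targets for these measures".

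Protocol section B.4 adds two further considerations, "including whether performance targets were reached and whether improvements were meaningfully large". It attributes the targets to the federal funders. Neither document gives a value for any target or for the size that would count.

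The only error limit in the SAP is: "Findings are considered statistically significant based on a $p < 0.05$, two-tailed test". It closes the paragraph on the RQ3 t-tests and the RQ4 regression, and no RQ1 test exists to which it could apply. On sample size, Protocol section B.2 says: "The projected enrollment and desired sample size for the study is 800 participants". No power or precision basis is given.

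**The concern.** The two secondary questions have an estimate, a test and a significance level. RQ1 has a set of graphs and an expected direction. Monthly averages move even when nothing has changed. With even enrollment, each plotted point rests on about 17 people. A reader who expects improvement and has no interval to consult cannot tell drift from change, and three metrics give three opportunities to see it.

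The SAP uses these trends to assess the association between the CQI process and the outcomes, so a conclusion is intended. Without a limit on chance, a favourable answer to RQ1 carries less information than it appears to.

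**Working it through.** The documents state no error rate, power or precision for RQ1, so there is no plan figure to reproduce.

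**Inputs from the documents**
- Three metrics, none ranked (Protocol B.1, B.4).
- 800 projected participants (Protocol B.2).
- Enrollment from 22 April 2021 to 15 February 2025 (Protocol B.2): 47 calendar months, and 800/47 = about 17 per month if even.

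**Assumptions** (the documents give no values): the correlation ρ between the estimated trends, a 30% event rate, and the cohort design effect D.

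**Step 1. Chance of at least one favourable trend when nothing has changed.** This applies only if any favourable trend, however small, in any one metric were read as improvement. Each trend then has probability 0.5 of the favourable sign.
- Independent metrics: 1 − 0.5³ = 87.5%.
- Equal correlation ρ: 1 − [1/8 + 3·arcsin(ρ)/(4π)].

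| ρ | Chance of at least one |
|---|---|
| 0 | 87.5% |
| 0.5 | 75.0% |
| 0.8 | 65.4% |
| 0.9 | 60.8% |
| 1 | 50.0% |

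A simulation (800 people over 47 months, least-squares slope, 20,000 runs) gives 87.2%, 74.9% and 65.2% for ρ = 0, 0.5 and 0.8. With 0.9 between dosage and attrition and 0.5 for survey response with each, the formula gives 70.3%.

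The independent case is implausible. Attrition is defined from workshop hours (Protocol Table 4), and the exit survey is taken at the final session (Protocol B.3), so all three metrics depend on staying in the program.

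**Step 2. Would a minimum size suffice?** For a rate p in n people enrolled evenly, the fitted start-to-end change has standard error √(12·p(1−p)/n). With p = 0.3 and n = 800: √(12 × 0.3 × 0.7/800) = √0.00315 = 5.6 points. A 5-point improvement is within one standard error. For one such metric, chance gives it with probability 1 − Φ(5/5.6) = about 19%.

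The answer depends on the contrast used. Comparing the first 400 with the last 400 enrollees, with each metric near 70%, the standard error is √(2 × 0.21/400) = 3.2 points. The chance that at least one of three metrics passes the minimum is:

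| Minimum | D = 1, ρ from 0 to 0.8 | D = 4, ρ from 0 to 0.8 |
|---|---|---|
| 2 points | 61% to 40% | 76% to 53% |
| 5 points | 17% to 11% | 53% to 34% |
| 10 points | 0.3% to 0.2% | 17% to 11% |

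A large threshold helps, but how much depends on a variance that the plan does not estimate.

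**Step 3. What an interval does.** If a 95% CI must exclude no change in the favourable direction, each metric has a 2.5% chance of a false improvement. For at least one of three, this is 1 − 0.975³ = 7.3% at ρ = 0, 6.3% at 0.5 and 4.9% at 0.8.

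**Step 4. Clustering.** Those figures need a correct standard error. Participants attend group classes in cohorts. If the interval ignores a design effect D, the chance of at least one false improvement with independent metrics is 1 − Φ(1.96/√D)³: about 16% for D = 1.5, 23% for D = 2 and 41% for D = 4.

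**The case against.** The strongest reply is that the evaluation is descriptive by title and by method, and that it sets no success rule. A reader might infer from the word joining the metrics in RQ1.1 that improvement in any one of the three counts as success, so that the plan has a false-positive rate of 65% to 88%. The documents do not support that. Protocol B.4 looks at change in each metric, Table 4 lists them separately, and the SAP speaks of the measures in the plural. Protocol B.4 also brings in targets and size of improvement, so a favourable slope of any size is not the stated criterion. The range is also conditional: 88% needs independence, and 65% is not a floor, since full overlap gives 50%. It is the chance of a misleading reading, not a type I error.

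Three further points stand. The funders' targets may have values that these documents do not show. The RQ1 sample is limited to participants at facilities that received CQI efforts (SAP, Analytic sample), so 800 may overstate it; a smaller sample would make the standard error larger. Requiring a multiplicity adjustment before any improvement is mentioned is debatable in a descriptive evaluation.

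None of this supplies the missing estimate or interval. A descriptive analysis can state its uncertainty, and this one is meant to inform a judgement about the CQI process.

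**Conclusion.** The concern holds in a limited form. RQ1 has three co-equal metrics, graphs as its only method, no estimate of change, no uncertainty limit and no number for a meaningful improvement. Chance drift can therefore be read as improvement.

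The 50% to 88% describes only the most permissive reading and rests on the assumed correlation; its upper end is unlikely. The 5.6-point standard error rests on 800 evenly enrolled participants, an assumed 30% rate and no clustering. It shows that modest differences over the study are within the range of chance.

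This is a worthwhile, low-cost improvement to the SAP. It does not show that the planned analysis must mislead. An interval would also leave attribution open: with no comparator, a clear change over time need not be due to CQI.

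**What to change.** Keep the graphs. Add to the SAP for RQ1, for each metric separately:

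- Regress the participant-level outcome on enrollment month: linear for percent of target hours, logistic or linear probability for attrition and survey response.
- Report the change from first to last enrollment month with a 95% CI that allows for clustering by workshop cohort.
- Describe a metric as improved only when the interval excludes no change in the favourable direction. Otherwise report 'no clear change'.
- State the funder's target as a number, give a figure for what counts as a meaningful improvement, and set the estimate and interval beside them.
- Use a multiplicity adjustment, such as Holm, only if the report makes a single claim that at least one of the three improved.
- Say in the report that the interval limits chance findings and does not show that CQI caused the change.

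The cost is some SAP wording and three regressions. The SAP (Data preparation) already merges dosage, client status and survey data in R by client ID. It does not mention a cohort identifier, so its presence in the export should be confirmed. The downside is that a modest real gain may be reported as 'no clear change'.

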- a. Report description – examine performance trends before and after an intervention at each site, looking for improvements and comparing to the relevant standards
- b. Purpose – assess results of interventions on performance outputs to determine whether improvements were made for the relevant standard
- c. Fidelity tracking –
  - i. Intended amount to be offered based on intended report timeline
  - ii. Actual amount offered (# CQI Team meetings scheduled on Outlook, # CQI Team meetings where Step 4 CQI Report presented to CQI Team, # Step 4 reports created)
- d. Dosage tracking –
  - i. Intended amount received – attendance of all members at CQI Team meetings for Step 4 Reports (i.e., number, names, roles)

- ii. Actual amount received – CQI Tracking Sheet for Team Attendance for Step 4 Reports
- e. Feasibility assessment –
  - i. Focus on utility and user-friendliness of Step 4 report
  - ii. CQI Team Survey for Step 4: administered each program year to staff on the CQI Team
  - iii. FCP Staff Survey for Step 4: administered each program year to all frontline staff who develop performance interventions with the CQI team

**Table 1.** Description of intended intervention components, content, dosage and implementation schedule, delivery, and focal populations

Components	Content	Dosage and schedule	Delivery	Focal population
CQI Process Step 1	Monitoring overall and recent program performance using nFORM operational reports, local evaluation survey data, and the query tool	Reports are prepared bi-weekly and discussed at bi-weekly, hour-long CQI team meetings	Virtual CQI team meetings are held bi-weekly on Tuesday mornings; the evaluation lead facilitates meetings, and Step 1 reports are presented by the evaluation lead and/or data manager	CQI team members (program director, program manager, evaluation lead, data manager(s))

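### RQ2 asks whether improvement differed between sites; the SAP assesses site trends after interventions from graphs but defines no per-site change with n and uncertainty, and no comparison of those changes

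*SAP*

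**What the plan says.** Protocol, section B.1, poses RQ2, which is not marked secondary: "Did meaningful improvements in primary workshop dosage, survey response rates, or program attrition rates vary by service site". It is limited to sites that worked on the same metric.

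Several passages plan a before/after reading by site:

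- Protocol, section A, describes the Step 4 reports as ones that "examine performance trends before and after an intervention at each site, looking for improvements and comparing to the relevant standards".
- Protocol, section B.4, says changes after intervention will be assessed, "including whether performance targets were reached and whether improvements were meaningfully large", and promises baseline data for targeted metrics at each site.
- The SAP, under Analytic approach, says site trends will be assessed for improvement since program start and directly after targeted interventions, which are marked on the graphs.

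The tool for all of this is a set of graphs of averages "by month since program start among participants who enrolled in that month". The comparison between sites is one sentence: "Site-level averages will be compared across the full study time period".

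On numbers, Protocol, section B.2, states "The projected enrollment and desired sample size for the study is 800 participants" and says the final report will give the "number of staff at each site, and number of participants at each site". On selection, section B.4 explains that "metrics that are already at or close to targets are not selected for intervention".

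**The concern.** RQ2 is a question about differences in change. To answer it, even descriptively, one needs a number for each site's improvement, some measure of how well that number is known, and a comparison of those numbers among sites that shared a target. Neither document defines a before or after window, a change statistic, an interval, a contrast of changes or a size that counts as meaningful. The per-site totals promised for the final report do not give the n behind a monthly point or a before/after period.

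The same SAP defines a change score and a test for the secondary RQ3, so the gap lies in the question that is not secondary.

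At stake is what gets reported as a site's response. The SAP states that metrics are expected to improve over time and right after interventions. With few enrollees per site and month, a rise or dip on a site graph can be taken as response or non-response when it is within chance variation. Selecting metrics that are not near target adds a pull upward, through regression to the mean, that the plan does not mention.

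**Working it through.** The plan states no precision, power or effect-size figure for RQ2 and no derivation of the 800, so there is nothing to reproduce. The checks below show what the planned comparison can and cannot distinguish, and roughly how precise a per-site change would be.

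**1. Does a full-period average answer RQ2?** Take three hypothetical sites with equal numbers before and after.

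| Site | Before | After | Full-period average | Change |
|---|---|---|---|---|
| A | 60% | 90% | 75% | +30 |
| B | 75% | 75% | 75% | 0 |
| C | 90% | 60% | 75% | −30 |

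The averages are identical and the changes opposite. If the SAP sentence means pooled averages, it does not address RQ2. If it means the monthly series side by side, the difference in change is judged by eye.

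**2. How many people are behind a monthly site point?** Inputs from Protocol B.2: 800 participants; enrollment from 22 April 2021 to 15 February 2025, which is 1,395 days or 45.83 months. Assumptions not in the documents: even intake, 3, 5 or 10 equally active sites, a binary metric at 75%. Ten at once is the extreme, since B.2 lists ten locations but says they varied over time.

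- Intake: 800 / 45.83 = 17.46 per month.
- Per site-month: 5.82, 3.49 or 1.75.
- Standard error of one point, √(0.75 × 0.25 / n): 18, 23 or 33 percentage points.

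**3. How precise is a six-month before/after change?** N per side = 6 × the monthly figure = 34.9, 20.9 or 10.5. Half-width for one site = 1.96 × √(2 × 0.1875 × D / N), where D = 1 + 7 × ICC for an assumed 8 people per class. For the difference in change between two equal sites, multiply by √2.

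| | 3 sites | 5 sites | 10 sites |
|---|---|---|---|
| One site, independent (D = 1) | ±20.3 | ±26.2 | ±37.1 |
| One site, ICC 0.05 to 0.10 | ±23.6 to 26.5 | ±30.5 to 34.2 | ±43.1 to 48.4 |
| Two-site difference, independent | ±28.7 | ±37.1 | ±52.5 |
| Two-site difference, ICC 0.05 to 0.10 | ±33.4 to 37.5 | ±43.1 to 48.4 | ±60.9 to 68.4 |

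The normal approximation is rough at N of about 10.

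**4. How far do these depend on the assumptions?**

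- At a 90% rate with the same N (0.09 in place of 0.1875, independent): ±14, 18 or 26 for one site.
- Dosage is a percent of hours, not a yes/no outcome. At a mean of 75%, p(1−p) is the largest variance it could have. With an assumed SD of 30 points the half-widths are again ±14, 18 or 26.
- Splitting the whole period in half, independent participants, rates from 90% to 50%: 5 sites (80 each side) give ±9.3 to 15.5 per site and ±13.1 to 21.9 for a difference in change. 10 sites (40 each side) give ±13.1 to 21.9 and ±18.6 to 31.0.

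**5. Regression to the mean.** Suppose a site's true rate never changes and it is selected because its before-window rate fell below a cut-off. The expected rise with no effect is p − E[X/N | X/N < cut-off], exact binomial, N = 35, 21 or 10.

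| True rate | Cut-off | N = 35 | N = 21 | N = 10 |
|---|---|---|---|---|
| 75% | 75% | 5.6 | 8.7 | 11.9 |
| 75% | 90% | 0.2 | 1.4 | 5.6 |
| 70% | 90% | 0.05 | 0.6 | 3.8 |

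This assumes that selection and the before value use the same window.

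**The case against.** The study calls itself a descriptive evaluation and plans no test for RQ2, so the absence of confidence intervals and interaction terms is not in itself an error. That stands, and no hypothesis test is asked for here. A descriptive statement that improvement varied by site still needs each site's improvement as a number with its n and uncertainty.

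A reader might infer that the SAP ignores change at sites altogether. The documents do not support that: assessment after interventions, site baselines, target attainment and a judgement of size are all promised. What is missing is their translation into a defined quantity and a comparison. Nor is it certain that the SAP means pooled averages; the sentence is ambiguous, and neither reading supplies the contrast.

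A reader might also take ±20 points as a minimum, or 12 points as the likely regression-to-the-mean effect. Neither follows. The first belongs to a 75% binary rate and six-month windows. The second puts the cut-off at the true rate in the smallest sites, and even N = 11 instead of 10 lowers it to 9.7. Selection may also rest on more data than the before window.

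Finally, a full mixed model could be unstable. Six months at one site is only about 4.4, 2.6 or 1.3 classes of an assumed 8 people per side, before any exclusions. That stands, so the model should be optional.

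**Conclusion.** The point holds in this form: the planned site-level reading is not carried through to a per-site change with n and uncertainty, or to a comparison of changes among sites that shared a target metric. RQ2 as worded would therefore be answered by eye or by averages that cannot show change. Whether a site reached its funder target is a separate descriptive question and is not affected.

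The absence of these definitions can be read directly from the documents. The size is illustrative only, because the documents give no site-by-month counts, rates or class sizes. Under the base assumptions, one site's change is known to about ±20 to ±37 points and a two-site difference in change to about ±29 to ±52. Both are narrower for rates near 90%, for longer windows and probably for dosage, and wider with clustering. The rise expected from regression to the mean alone runs from under 1 to about 12 points, depending on cut-off, true rate and window. The SAP should be changed, but this is not a flaw that invalidates the evaluation.

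**What to change.** Add to the SAP, for RQ2:

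- **Per-site table.** For each site and targeted metric, give n, the before value, the after value and their difference with a 95% CI. Use a pre-set window around the intervention date or cohort, which the evaluators already log (Protocol, implementation study, section 3). State how overlapping interventions and classes already under way on a start date are handled. Allow for clustering by workshop cohort where the data permit.
- **Between-site comparison.** Among sites that targeted the same metric, show the differences in change with CIs, labelled descriptive. A site-by-period model with a random cohort effect is optional.
- **Meaningful size.** State what change counts as meaningful before running the comparison, and disclose that the metrics had already been seen in CQI reports (Protocol B.3).
- **Graphs and caveat.** Keep the monthly graphs as illustration with n at each point. Note that metrics near target were not selected, so gains may partly be regression to the mean; the interval does not correct for this.

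The cost is a short SAP addition and modest coding. No new data are needed, since client-level programmatic records are already to be merged by ID (SAP, Data preparation). The downside is wide intervals: between-site variation will probably have to be reported as imprecise, and RQ2 may not be settled.

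### Full-period site averages can mix site with calendar time where sites ran in different windows, and they do not measure the improvement RQ2 asks about

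*SAP*

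**What the plan says.** RQ2 (Protocol, B.1 Research questions) asks whether meaningful improvements in dosage, survey response or attrition varied by service site, "for sites that focused on improving the same metrics".

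The SAP (Analytic approach) graphs monthly averages "by month since program start among participants who enrolled in that month". It then says that "trends in site-level averages will be assessed both for improvements since program start and immediately following the implementation of targeted interventions", with interventions marked on the graphs. The next sentence is the one at issue: "Site-level averages will be compared across the full study time period". The paragraph closes with the expectation that "average metrics are expected to improve over time and immediately following interventions". The SAP's Analysis approach states the same expectation for the program as a whole: "we would expect that program implementation would get stronger over time".

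On the sites themselves, the Protocol (B.2 Outcomes evaluation enrollment) says "Program service locations have varied throughout the implementation of the program but have included" and lists ten locations, counting virtual delivery as one. It gives no opening or closing dates.

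**The concern.** Three statements do not fit together: the list of sites changed, the metrics are expected to rise with calendar time, and site averages are to be compared over the whole period. A site that was open for only part of the study contributes only the months it had. If the comparison uses one average per site, a difference between sites can be a difference between years. Nothing in the RQ2 restriction (same target metric) or the analytic sample (facilities that received CQI efforts) requires sites to share an operating period.

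There is also a mismatch with the question. RQ2 is about improvement, and a full-period average is a level. A site can have a high average without having improved, or a low one despite a clear gain. Assessing improvement since program start also has no clear meaning for a site that was not open at program start.

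RQ2 is one of the two main outcome questions (RQ3 and RQ4 are labelled secondary), so what is at stake is which sites the final report describes as having improved.

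**Working it through.** The plan gives no expected effect, site-level rate or site dates, so there is no figure of its own to reproduce. The check asks how far two identical sites could differ under stated assumptions.

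**Inputs from the documents**
- Enrollment window (Protocol, B.2): "Enrollment into the study began April 22, 2021 and is estimated to conclude February 15, 2025". This touches 47 calendar months, numbered 0 to 46.
- Time axis: month since program start (SAP, Analytic approach).
- Projected enrollment of 800 and ten listed locations (Protocol, B.2).

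**Assumptions**
- A gain of G percentage points shared by all sites, linear over the 47 months, with even enrollment.
- Early site open in months 0–11 (mean 5.5), late site in months 35–46 (mean 40.5), third site open throughout (mean 23).

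**Shared calendar gain.** Site average = base + G × (mean month ÷ 46).
- Late − early = G × (40.5 − 5.5)/46 = 0.761 G
- Late − throughout = G × (40.5 − 23)/46 = 0.380 G
- With 24-month windows (means 34.5 and 11.5): late − early = G × 23/46 = 0.5 G

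| G (points over the study) | Late − early, 12-month windows | Late − early, 24-month windows | Late − throughout |
|---|---|---|---|
| 0 | 0 | 0 | 0 |
| 5 | 3.8 | 2.5 | 1.9 |
| 10 | 7.6 | 5.0 | 3.8 |
| 20 | 15.2 | 10.0 | 7.6 |

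For attrition a lower value is better, so the sign reverses but the late site still looks better.

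**Gain tied to time since the site opened.** The late and early sites then have the same average (gap 0). The late site falls below the site open throughout by 0.380 G: 1.9, 3.8 and 7.6 points for G = 5, 10 and 20.

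**Mixture.** Take a calendar gain of 10 plus a step of S points six months after each site opens. Late − early stays at 7.6. Late − throughout = 3.80 − S × (41/47 − 6/12) = 3.80 − 0.372 S, which is 1.9 at S = 5, 0.1 at S = 10 and −1.4 at S = 14. The sign depends on where the improvement comes from.

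**What the fix does.** Use six months either side of each site's intervention. The two windows are centred six months apart, so shared drift adds G × 6/46 to each site's change: 1.3 points at G = 10. Both sites get the same amount, so it cancels between them. If one site used 12 months either side (10 × 12/46 = 2.6), the residual difference is 1.3 points, against 7.6 for the 12-month early and late averages. An average over months in which both sites were open has no gap from shared drift at any G, but it is unavailable where there are no shared months.

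**Counts.** 800/(10 × 46 months) is about 1.7 enrollees per site-month if evenly spread, so six months either side is about 10 people per window.

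**The case against.** The strongest reply is that the sentence need not mean one pooled figure per site. The outcome is a monthly series and the preceding sentence is about trends, so it may mean that site series are laid side by side, in which case a 2021–22 line and a 2024 line are visibly at different dates. Several other provisions also help:
- Protocol B.4 (Outcome measures) assesses change after interventions and gives baseline data for targeted metrics at each site.
- Step 4 of the CQI process examines each site before and after its intervention.
- Metrics already at or near target are not selected for intervention, so a late site that starts near target would usually not enter the comparison for that metric.
- The analysis is descriptive, with no test and no planned ranking of sites.

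Most of this stands, and it limits the problem. It does not remove it. The SAP does not say which reading applies. Non-overlapping series still leave site and year inseparable. The baselines are offered to deal with ceiling and floor effects, not unequal windows. The selection rule does not exclude a site that inherits only part of a program-wide gain. No provision says how sites with different operating periods are to be compared.

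A reader might go further and infer that the plan favors late-opening sites and would name them as the places where CQI worked. The documents do not support that. They do not show which sites opened late or closed early, or that sites sharing a target metric failed to overlap. A late site with a high level and no change would show a high baseline and no gain after its intervention.

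**Conclusion.** The point holds in a limited form. If site averages are pooled over the full period, sites that ran in different windows can differ because of when they ran, and the planned graphs, baselines and post-intervention review only partly offset this. On either reading of the sentence, a full-period level is not a measure of improvement, which is what RQ2 asks about.

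Direction and size are unknown. They rest on assumptions about drift and site dates that the documents do not supply. Under a shared gain of 5 to 20 points the illustrative gap is 3.8 to 15.2 points for 12-month windows at opposite ends of the study, and 1.9 to 7.6 against a site open throughout. Under purely site-specific gains it is zero or reversed. A single headline such as 14 points would need 5 points per year (5 × 46/12 = about 19 over the study) and windows near the two extremes, so it should not be read as an estimate.

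This affects the interpretation of a descriptive comparison, not a hypothesis test. It is worth correcting because the correction is cheap.

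**What to change.** Replace the SAP sentence with:

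> For sites that targeted the same metric, the between-site comparison will be of each site's change from its own pre-intervention months to its post-intervention months, aligned on its intervention date. Each site's first and last enrollment months and number of participants will be shown. Full-period site averages will be descriptive only and will not be used to compare sites whose operating periods differ; where periods overlap, averages over the shared months may be shown as a supplement.

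Sites without both pre- and post-intervention cohorts should be listed descriptively and not compared. Where data allow, use the same number of months either side at each site, so that shared drift enters each change equally. Do not subtract the concurrent change at other sites: they may also be receiving CQI, and the subtraction could remove the effect of interest.

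The change needs SAP wording only. Enrollment month and site are already needed for the graphs, and the evaluators already document when and where each intervention starts (Protocol, Implementation study, Data sources and data collection). The cost is that fewer sites can be compared and that, at about 10 people per six-month window, the changes will be imprecise. Counts should therefore stand beside every change.
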